Perioperative Intravenous
Lidocaine Infusion for Patients
Undergoing Laparoscopic and
Open Pancreatectomies

NCT# 02623803

March 30, 2016

Research Protocol Submission Template

Title of the study: Perioperative Intravenous Lidocaine Infusion for Patients Undergoing Laparoscopic and Open Pancreatectomies

Principal investigator:

[name].

Co-investigator(s):

[name] M.D.

[name] M.D.

[name]

[name], DNP, RN

[name].

[name]

Study coordinator(s):

[name], B.S.

[name].

Protocol version / date

Version 3. March 30, 2016

Abstract

DESCRIPTION:

Patients undergoing major intra-abdominal surgeries, such as pancreatectomies, face the challenge of postoperative pain control, return of bowel function, and postoperative ileus. Epidural analgesia offers benefits in these areas; however, it is utilized rarely at our institution, because it is an invasive procedure with risks and potential complications.

Several studies have demonstrated improved patient rehabilitation after abdominal surgery in which patients received perioperative intravenous (IV) infusion of lidocaine. As an adjunct to multimodal analgesia, IV lidocaine infusion in colectomy patients has been shown to decrease postoperative pain, opioid consumption, postoperative ileus, and length of hospital stay. The purpose of this study is to evaluate if an IV lidocaine infusion will provide clinical benefits to pancreatectomy patients with regard to analgesia and return of bowel function.

Different titrations of the IV lidocaine infusion for postoperative analgesia have been reported without side effects of local anesthetic toxicity (8).

Research Plan

1. Specific Aims

The objective of this study is to see if perioperative IV lidocaine infusion improves postoperative analgesia and return to bowel function in patients undergoing open and laparoscopic pancreatectomies. If analgesia is improved and return of bowel function is expedited in this patient population, then a standardization of practice will be implemented to improve patient outcomes and reduce hospital length of stay.

2. Background and Significance

The analgesic properties of local anesthetics have been well documented in the literature (1, 2). Proposed mechanism for systemic analgesia include antinociceptive effects by blocking sodium and potassium channels, pain modulation in the CNS by inhibiting NMDA and NK receptors, and antiinflammatory properties (17). Intravenous infusions of lidocaine have been used in several types of surgeries, including orthopedic, breast, abdominal, and gynecological surgeries. Intra-abdominal surgeries involving bowel resection have shown the most favorable outcomes in improved analgesia and improved rate of return of bowel function (3, 4, 5). Significant evidence also demonstrates that epidural analgesia helps with pain control and return of bowel function in patients undergoing a variety of open and laparoscopic intraabdominal cases (6, 7). However, routine use of epidural analgesia is implemented infrequently due to an epidural being an invasive procedure with its own associated risks and complications. Based on this known information, an intravenous lidocaine infusion protocol is being proposed to assess post-operative pain control and improved return to bowel function in patients undergoing open and laparoscopic pancreatectomies.

3. Progress Report and Preliminary Studies

Lidocaine infusion during pancreatic surgery, to date, has not been studied. A few trials in cooperation with [name] have taken place, since January 2015., the patients demonstrated subjectively improved pain control in the recovery room and decreased opioid consumption. Plasma lidocaine levels measured in 8 patients averaged 2.26 ug/ml (range 1.2 – 3.3 ug/ml), and they were consistently below toxic levels and no side effects were noted nor reported by the patient.

4. Research Design and Methods

Study Design or Overview –

50 patients will be recruited in the study. Prior to the day of surgery, all patients are seen by their surgeon for their pre-surgical evaluation. At the time, the patient will be consented to participate in the study involving lidocaine infusion to improve post-operative pain and control and return of bowel function.

As is current practice at our institution for intra-abdominal cases including pancreatectomy surgery, an ***Enhanced Recovery Pathway (ERP)*** will be utilized as outlined below:

Pre-operative multimodal non-opioid analgesics (single dose P.O. with water):

- Celecoxib 400 mg
- Gabapentin 600 mg
- Acetaminophen 1000 mg

Intraoperative management:

- Maintenance of general anesthesia will be standardized to sevoflurane with air/oxygen mixture at 2 L/min

- Fentanyl will be the only opioid use at induction of anesthesia and during the surgery.
- Fluid administration goals – (modified as clinical circumstances dictate)
 - 500 mL per hour for laparoscopic cases
 - 800 mL per hour for open cases
 - Phenylephrine or ephedrine boluses as needed to maintain mean arterial pressure (MAP) > 60 mmHg
- Postoperative nausea and vomiting (PONV) prophylaxis
 - Dexamethasone 4 mg I.V. at anesthesia induction (one dose)
 - Ondansetron 4 mg I.V. 30 minutes before emergence from anesthesia (one dose)
 - For patients with a history of PONV, droperidol 0.625 mg I.V. or promethazine 12.5 mg I.V. will be given as a third anti-emetic agent.
- Nasogastric (NG) or Orogastric (OG) tube is to be removed at the end of the case unless specified by the surgical team.

Postoperative non-opioid analgesics:

- Acetaminophen 1000 mg PO every 6 hours
- Ketorolac 30 mg IV every 6 hours to start after the surgery (total of 4 doses)
 - For patients >65 years old or <50 kg use 15 mg of ketorolac IV
- Ibuprofen 800 mg PO every 6 hours after the last ketorolac dose
 - For patients >65 years old or <50 kg use 400 mg of ibuprofen PO

Opioid analgesia

- Patient Controlled Analgesia (PCA) with IV hydromorphone will be utilized in the first 24 hours
- IV or PO hydromorphone will be used for breakthrough pain

Diet:

- Soft, low residue diet evening of POD #0
- Advance to low fat diet excluding raw vegetables and fresh fruit at 0700 on postoperative day 1 if patient without nausea.
- If patient is diabetic, advance to diabetic diet excluding raw vegetables and fresh fruit at 0700 on postoperative day 1 if patient without nausea.

Activity:

- Out of bed greater than 1 hour, including 1 or more walks and sitting in chair within 2 hours of reaching the surgical floor
- Day after surgery and until discharge, out of bed greater than 6 hours, including 4 or more walks and sitting in chair
- All meals out of bed

Intraoperative lidocaine infusion protocol

On the day of surgery, the patient will be randomly assigned to either the lidocaine infusion (2 grams of lidocaine in 500cc D5W) study group (n=25 patients) or the control group (n=25 patients) who will receive 500cc of D5W infusion with no lidocaine. Pharmacy will handle randomization of patients. The patient, the surgeon, the anesthesiologist and the postoperative

nursing staff will be blinded to which group patients were assigned. The infusion bag will be dispensed by pharmacy based on the randomization protocol and labeled “Lidocaine Infusion Study” with the corresponding IRB number.

The anesthesiologists assigned to the case will begin with a bolus infusion of lidocaine, 1.5 mg/kg (max 100 mg of lidocaine) at the time of anesthesia induction, followed by a continuous infusion set at 1.5 mg/kg/hour from the IV bag labeled “Lidocaine Infusion Study”

Actual body weight will be utilized in the dosing of lidocaine with a limit of 100mg of lidocaine bolused and maximum infusion rate not to exceed 3mg/min. Patients with BMI >40 are excluded from the study.

Intraoperative opioids will be limited to fentanyl in order to standardize intraoperative opioid requirements and intraoperative ketamine will be avoided. The surgical team is instructed not to infiltrate the surgical wound with local anesthetic during or at the end of surgery. The lidocaine infusion will be continued in the PACU. The nurse in the PACU will be instructed to discontinue the infusion when the patient meets PACU discharge criteria. The nurse and the surgical team are instructed not to use fentanyl during the postoperative period for analgesia. Prior to the discontinuation of the infusion, every patient will have a lidocaine level drawn before leaving the PACU.

Intra-op and PACU *stopping* rules

- If unstable arrhythmias are noted in the OR/PACU, the infusion will be stopped and a plasma lidocaine level will be drawn.
- If symptomatic bradycardia and significant hypotension refractory to treatment, consider stopping the infusion.
- If significant intra-operative hemorrhage (1 body blood volume), consider stopping the infusion.
- If the patient requires ICU admission after surgery due to intraoperative complications, the infusion will be stopped at the end of surgery.
- If the patient in the PACU demonstrates sudden changes in mental status, convulsion, or coma, the infusion will be stopped and a lidocaine level will be drawn.
- If mortality or major complications were to occur during the study, the cases will be reviewed by the primary investigator and co-investigators to determine the cause and if poor outcome is related to the study. All such cases will also be reported to IRB.

Baseline Assessments

1. Pain at rest and with coughing via a Numerical Rating Scale (NRS) – completed on the day of surgery in preop holding area
2. Quality of Recovery (QoR-15) questionnaire – completed at the time of consenting or preop on the day of surgery.

Assessment and management in the PACU (day of surgery)

1. Pain scores via a Numerical Rating Scale (NRS) will be assessed in the PACU at rest and with coughing at the time of PACU arrival and at 30 minute intervals (Appendix A). (15) If the

patient is too somnolent upon arrival in the PACU and unable to participate, then the findings are to be documented as such (i.e., unable to participate).

2. Upon arrival to PACU and at 30 minutes, patient's level of consciousness will be assessed via the Richmond Agitation-Sedation Scale (RASS) (Appendix B).
3. Upon arrival to PACU and at 30 minute intervals the patient will also be evaluated by the PONV Impact Score (Appendix C).
4. Fentanyl use will be avoided in the PACU.
5. Total opioid requirements in the PACU will be noted. Converted to morphine equivalents as per Table 1.
6. Use of ketorolac or acetaminophen will be noted
7. Incidence of nausea/vomiting and administered treatment in PACU will be noted.
8. PACU length of stay (defined as the time from PACU admission until discharge criteria are met as per PACU nurse evaluation and documentation).
9. At time of the patient meeting discharge criteria in the PACU, lidocaine infusion will be stopped and lidocaine plasma levels will be drawn in all patients in order to keep the PACU staff blinded.

Assessment of the patient on the floor

1. The patient will be assessed by floor nurse on POD #0 at 8 PM and POD #1 at 8 AM and 8PM.
2. Pain will be assessed via the NRS scale at the prescribed times at rest and with coughing. Nurses will also rate the patients' average pain on a scale from 0 to 10 (0=no pain; 10=worst pain ever experienced) in the past 12 hours, or since their time of surgery if it is POD #0.
3. The current level of consciousness will be evaluated using the RASS score.
4. At 24 hours from the time of arrival to PACU, the patient's quality of recovery will be evaluated by the one of the study coordinators via a validated 15-question Quality of Recovery (QoR – 15) questionnaire.
5. At 24 hours from the time of arrival to PACU, the score on PONV Impact Scale will be obtained.
6. Need for nasogastric (NG) tube during hospital stay will be noted.

Return of bowel function

During the patients hospital stay, the time to first flatus and first bowel movement will be noted as per progress note of the surgical team. The surgical team is specifically instructed to ascertain these recovery milestones every morning during clinical rounds.

Additional data include

1. Duration of surgery (in minutes)
2. Time when PACU discharge criteria are met (in minutes)
3. Length of hospital stay
4. QoR-15 questionnaire via telephone call 2 to 3 weeks from the day of surgery.

b. Study Subjects.

Inclusion criteria:

- All adult patients undergoing elective open or laparoscopic total pancreatectomies and pancreatoduodenectomies (i.e., Whipple procedure), and participating in the ERP.
- Age 18 – 80 years old
- ASA class I – III
- BMI < 40
- Ability to understand and read English

Exclusion criteria:

- Not able or willing to sign consent
- Intolerance or allergy to opioids, NSAIDS, acetaminophen, or amide-type local anesthetics (i.e., lidocaine).
- History of epilepsy or currently receiving treatment for seizures
- Severe hepatic insufficiency (Child-Pugh Score C) – if documented in patient's medical history
- Renal insufficiency (creatinine clearance less than 30 mL/minute) – if documented in patient's medical history
- Advance heart failure
 - NY Heart failure stage 3 or greater
 - Ejection function <30%
- Cardiac arrhythmias:
 - 2nd and 3rd degree heart block, sick sinus syndrome, symptomatic bradyarrhythmias, Wolff-Parkinson-White (WPW) syndrome, or Stokes-Adams syndrome
 - Left bundle branch block or bifascicular block
 - *Not to exclude* patients the following conditions unless clinical circumstance dictate:
 - Atrial fibrillation or atrial flutter
 - Presence of Implantable Cardioverter Defibrillator (ICD), or pacemakers
- Patients on anti-arrhythmic therapy (i.e., digoxin, amiodarone, flecainide, lidocaine, sotalol, etc.)
 - *Not to exclude* patients on beta blockers (i.e., metoprolol, atenolol, etc.) unless clinical circumstance dictate
- Patients with active psychiatric disorders (such as schizophrenia, bipolar disorder) or cognitive dysfunction
- Pregnancy or lactating
- Enucleation, central, and distal pancreatectomy
- Opioid tolerance (defined as consumption of greater than 30 mg of oxycodone per day)

Sample Size – The study will include 50 patients to be randomized and blinded in two groups of 25 patients each. No prior studies have been conducted on patients undergoing pancreatectomies and receiving a lidocaine infusion. However, several studies have shown statistical significant improvement in postoperative pain control and reduction of opioid requirement with the use of lidocaine infusion for intraabdominal surgeries, and often requiring 20 to 50 patients. (8) Additional 7 subjects will be screened to reach target accrual of 50 patients.

Data Collection –

Preoperative

1. Age, Sex, ASA Physical Status, Height, Weight, and BMI
2. Analgesics including opioids, NSAIDs, and/or acetaminophen (as per home medication list)
3. Current pain score as per NRS scale
4. QoR - 15

Intraoperative

1. Total pancreatectomies or pancreatoduodenectomies (as per post-op surgical note)
2. Open or laparoscopic (note if the case was converted to open)
3. Surgeon 1 or 2 (Drs. [name] or [name])
4. Duration of surgery
5. Duration of lidocaine infusion (time from induction to discontinuation in the PACU)
6. Total amount of fentanyl used in the OR.
7. Amount of anesthetic gas used (sevoflurane at 2L/min of fresh gas flow)
 - i. At the conclusion of the surgery, the anesthetic gas consumption will be as recorded by our Apollo Anesthesia Machine – Dräger
 - ii. Hourly vapor anesthetic requirements will be determined by the total anesthetic gas used divided by duration of the case (intubation time to surgery end time)

PACU

1. Pain score on arrival to PACU and at 30 minutes at rest and with coughing using the NRS scale
2. RASS score on arrival to PACU and 30 minutes after PACU admission
3. Incidence of PONV as reported and treated by PACU nurse.
4. Opioid requirements as converted into morphine equivalents (Table 1)
5. Use of acetaminophen or NSAIDs
6. Total PACU time (arrival to PACU until meeting discharge criteria as per PACU nurse)
7. Time of the discontinuation of the infusion
8. Plasma lidocaine level at the discontinuation of the infusion

Table 1: Morphine-equivalent based on an opioid equianalgesic

Opioid Drug (mg)	Administered	equianalgesic ratio to oral morphine
Morphine	PO	1:1
Morphine	IV	3:1
Oxycodone	PO	1.5:1
Hydrocodone	PO	1:1
Fentanyl	IV	300:1
Fentanyl	Transdermal	70:1
Oxymorphone	PO	3:1
Oxymorphone	IV	30:1
Hydromorphone	IV	18:1
Hydromorphone	PO	4:1
Tramadol	PO	0.3:1

Postoperative day 0 -1

1. POD #0 at 8PM and POD #1 at 8AM and 8PM:
 - a. Current pain via NRS scale at rest, coughing, and average of the past 12 hours or since surgery if POD #1
 - b. Current RASS score
2. At 24 hours from arrival to PACU
 - a. Quality of Recovery (QoR – 15) questionnaire with assistance of a co-investigator (16).
 - b. Opioid requirements as converted into morphine equivalents
 - c. Acetaminophen or NSAIDs use

Hospital stay

1. First time to flatus (in days)
2. First time to bowel movement (in days)
3. Presence of NG tube (in days)
4. Length of hospital stay (in days)

Outpatient follow up

1. QoR – 15 via telephone call

Data Handling – Data will be entered into a secure REDCap database by study assistant. Principal Investigator will verify data to ensure accuracy.

Data Analysis - A t-test will be used to analyze mean differences in NRS scores, opioids requirements, and return of bowel function between groups. Complication rates will be analyzed using a Chi-squared analysis.

Feasibility and Time Frame – About 100 pancreatectomies per year are done at our institution. Anticipating that 50% of patients are not enrolled due to the exclusion criteria or unwillingness to

participate in the study, the anticipated time frame of patient recruitment for this study will be one year.

Strengths – The study focuses on a patient population that frequently has difficulties with postoperative pain control, delayed return of bowel function and ileus, which are often exacerbated by opioids. This study will determine if incorporating lidocaine infusions will be of help to this patient population. Also, the proposed study has been previously performed on similar surgical procedures with demonstrating improved postoperative analgesia and without any adverse outcomes (8, 9, 10). All drugs and personnel required for this study are readily available and in place at Mayo Clinic.

Limitations – Even though highly unlikely, the potential for local anesthetic toxicity exists. During the patients' intraoperative course, EKG, blood pressure, and pulse oximeter will be closely monitored for any potential signs of arrhythmias. If there is any suspicion of local anesthetic toxicity, the infusion will immediately be discontinued, the anesthesiologist taking care of the patient will be unblinded, and a serum level of lidocaine will be drawn at that time if appropriate. Close monitoring of the patients will also continue to take place in the PACU, as is the standard of care.

5. Human Subjects

Detailed Description: All human subjects will meet the criteria aforementioned and will be undergoing open or laparoscopic total and subtotal pancreatectomies.

Population: Patients who are scheduled to undergo either open or laparoscopic pancreatectomy will be given the opportunity to provide an informed consent for this study. Patients will be selected without regard to race or gender. We plan to enroll 50 patients who will meet inclusion and exclusion criteria.

Research Materials: Data elements will be obtained from the patients' medical record and entered into REDCap database

Recruitment of Subjects: Patients will be recruited at the surgeon's office, during their pre-operative visit. The prospective candidates for the study will be approached by the study team member. Patients will be given information regarding the drug, the potential benefits, and complications of being enrolled in the study. Patients will be given adequate time to review the consent form, ask questions, and make an informed decision to either participate or decline.

Potential Risks: Even though highly unlikely, the potential for unknown local anesthetic toxicity exists. Early or mild sign and symptoms of toxicity include sudden dizziness, confusion, tinnitus, metallic taste, and numbness or tingling of fingers, toes, or lips. These signs and symptoms may progress to convulsions, unconsciousness, sudden hemodynamic instability, cardiac arrhythmias, or cardiac arrest. To date, there are no documented cases of morbidity or mortality associated with IV lidocaine analgesia.

Every participant in this study will be closely monitored by the anesthesia providers. During their intraoperative course and in the PACU, EKG, blood pressure and pulse oximeter will be closely monitored for any potential signs of arrhythmias. If there is any suspicion of local anesthetic toxicity, then the infusion will immediately be discontinued and a serum level of lidocaine will be drawn at that time. The study team members will become unblinded to determine the relatedness of side effects to the study drug.

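### First flatus and first bowel movement are asked about once each morning and recorded in days with no time origin, a small and cheaply reduced loss of precision on part of the objective

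*Combined protocol and SAP*

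**What the plan says.** Section 1 (Specific Aims) asks whether the infusion "improves postoperative analgesia and return to bowel function in patients undergoing open and laparoscopic pancreatectomies", so bowel function stands beside analgesia in the objective.

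Section 4, Return of bowel function, takes both milestones from the surgical team's progress note: "The surgical team is specifically instructed to ascertain these recovery milestones every morning during clinical rounds".

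Section 4, Data Collection, Hospital stay items 1 and 2, lists "First time to flatus (in days" and "First time to bowel movement (in days" (closing brackets omitted). Neither item asks for a clock time or says when time zero is.

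Other timed data are finer or anchored. The additional data in section 4 include "Duration of surgery (in minutes" (closing bracket omitted), and the time when PACU discharge criteria are met is also in minutes. The first postoperative QoR-15 and the opioid total are taken 24 hours from PACU arrival.

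Under Data Analysis, "A t-test will be used to analyze mean differences in NRS scores, opioids requirements, and return of bowel function between groups". Under Sample Size, "The study will include 50 patients to be randomized and blinded in two groups of 25 patients each". No effect, SD, alpha or power is given for bowel function.

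**The concern.** With one enquiry a day and a unit of days, an event just after one round and an event just before the next receive the same value, although they may be almost 24 hours apart. With no time origin, a patient whose surgery ends at noon and one whose surgery ends in the evening share day 0.

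Both features add variation unrelated to treatment. What is at stake is precision: a wider interval for the bowel-function difference and less power to detect a difference of hours. The point concerns patients who have the event while in hospital. How to handle those who do not is a separate question.

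**Working it through.** **Inputs from the documents.** 25 per arm; two-sample t-test on means; one enquiry each morning; unit of days. The plan has no power figure for bowel function to reproduce.

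**Assumptions.** Two-sided 5% test; true event time normal with mean 72 h after surgery and SD 12, 18, 24 or 36 h; surgery ending evenly between 12:00 and 20:00; each event booked to the next 07:00 round; true difference 12 h.

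**Step 1: added variance.**
- A 24-h grid adds about 24²/12 = 48 h².
- Counting from calendar day 0, not from the end of surgery, adds about 8²/12 = 5.3 h².
- The total is about 53.3 h². Relative to SD² this is 53.3/144 = 37%, 53.3/324 = 16.5%, 53.3/576 = 9.3% and 53.3/1296 = 4.1%.

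Simulating the booking rule directly gives the ratios in the table, close to these.

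**Step 2: effective size and power.** Effective n per arm = 25 / variance ratio. Power is from the noncentral t with 48 df and noncentrality 12 / (SD × √(2/25)). For SD 18 h this is 12/(18 × 0.283) = 2.36 with exact times. With daily recording the SD becomes 18 × √1.165 = 19.4 h and the noncentrality 2.18.

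| True SD (h) | Variance ratio | Effective n per arm | Power, exact times | Power, daily |
|---|---|---|---|---|
| 12 | 1.351 | 18.5 | 93% | 85% |
| 18 | 1.165 | 21.5 | 64% | 57% |
| 24 | 1.094 | 22.9 | 41% | 38% |
| 36 | 1.039 | 24.1 | 21% | just under 21% |

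**Step 3: bias.** A second simulation used skewed (gamma) times with a control mean of 3 days, SDs of 0.5 to 2.0 days and surgery ending between 12:00 and 18:00. A true difference of 0.5 day came back as 0.498 to 0.513 day. Over all differences tried (0.25 to 1.0 day) the error stayed within about 0.03 day.

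**Step 4: what recalled times would recover.** Let the recall error be random with SD e, so the variance is SD² + e². At SD 18 h:
- e = 6 h: 324 + 36 = 360 h², power about 59%, against 57% daily and 64% exact.
- e = 3 h: 324 + 9 = 333 h², power about 62–63%.
- Break-even is near e = √53.3 = 7.3 h. A recall error that large would cancel the gain.

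**The case against.** **The size depends on an SD that the plan does not give.** The trial pools open and laparoscopic cases, and total pancreatectomy with pancreatoduodenectomy, in patients described as prone to delayed bowel function. That points to a wide spread, where the loss is small: about 3 points at SD 24 h and under 1 point at SD 36 h. Power there is already low for reasons unrelated to the recording unit. This stands.

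**Patients cannot supply exact times.** They recall the event at the next round, and hydromorphone PCA is used for the first 24 hours. This also stands, and Step 4 allows for it. It does not remove the case for asking, because an approximate time can always be collapsed to a day, whereas a day cannot be expanded afterwards.

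**Stronger readings that the documents do not support.**
- A reader might infer that the grid is as coarse as any plausible treatment effect. No effect is stated for bowel function, and the comparison would use the wrong yardstick: the loss depends on the grid's variance relative to the between-patient SD.
- A reader might infer that daily recording saves nothing. It is a simple, low-burden procedure. Scheduled floor-nurse assessments end at 8 PM on POD #1, so prospective timing beyond that would be new work.
- A reader might take whole days as stated. The text says only days. Whole days is the natural reading of one morning enquiry with no clock time, but fractions are not barred. The missing time origin needs fixing on either reading.

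**Conclusion.** The point holds as a minor, cheap improvement. Daily ascertainment, a unit of days and an undefined time zero are all in the plan, and they fall on part of the stated objective. The cost is random noise that favours neither arm, equivalent to losing about 1 to 6.5 patients per arm over the assumed SDs of 36 down to 12 h. For a 12-h difference that is from under 1 to about 9 points of power. It matters mainly if the true SD is about 18 h or less.

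These figures rest on assumed SDs, an assumed difference, assumed surgery end times and a two-sided 5% test, since the documents supply none of them. They are upper limits on the benefit: with a 6-h recall error at SD 18 h, only about 2 of the 6.5 points lost come back. The recording unit does not invalidate the bowel-function comparison, and it is not the main limit on power. At SD 24 h, exact times would still give only 41%.

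**What to change.** 1. In Data Collection, Hospital stay items 1 and 2, replace the unit of days with the date and approximate clock time of first flatus and of first bowel movement. Have the team ask for these at the same morning round and write them in the progress note.
2. Define time zero as the end of surgery and add surgery end date and time to the Intraoperative list. That time is currently mentioned only within the calculation of hourly anesthetic gas use and is not a listed field.
3. In Data Analysis, state that return of bowel function is analysed in hours from surgery end. If only the interval between two rounds is known, record that interval and use its midpoint in the t-test. For those patients the 24-h grid remains.

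Cost: one more question at a round already made, one added field and a change of field format. No new visits or staff are needed. The downside is that some times will be approximate.

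### The t-tests for NRS scores and opioid requirements make no use of baseline pain, preoperative opioid use or surgical approach; a prespecified two-covariate ANCOVA is a cheap improvement, of a size the documents do not fix

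*Combined protocol and SAP*

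**What the plan says.** Section 4, Data Analysis, states: "A t-test will be used to analyze mean differences in NRS scores, opioids requirements, and return of bowel function between groups". It names no covariate, and no regression, ANCOVA or stratified analysis appears elsewhere. Neither description of randomisation (section 4, Intraoperative lidocaine infusion protocol; section 5, Protection) mentions stratification. Patients are to be "randomized and blinded in two groups of 25 patients each" (Sample Size).

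Three likely predictors are recorded:

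- **Baseline pain.** Baseline Assessments asks for "Pain at rest and with coughing via a Numerical Rating Scale (NRS") in the preoperative holding area. The preoperative list under Data Collection has only "Current pain score as per NRS scale", without the split into rest and cough.
- **Preoperative opioid use.** Data Collection takes analgesics, including opioids, from the home medication list and describes no dose field. The exclusion criteria remove only patients above 30 mg of oxycodone per day, so users and non-users can both enrol.
- **Surgical approach.** The intraoperative list has "Open or laparoscopic (note if the case was converted to open"). Both approaches are eligible.

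Opioid outcomes appear in the PACU list and again at 24 hours: "Opioid requirements as converted into morphine equivalents". NRS outcomes include scores at rest and with coughing, and a floor rating of average pain over 12 hours.

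**The concern.** Whatever part of the spread in pain scores and opioid totals is due to baseline pain, prior opioid use or approach stays in the error term of a t-test. With 25 per arm and no stratification, neither the design nor the analysis uses that information, although it is already collected. Adjustment could recover some precision without recruiting anyone. Fixing the model now would also prevent covariates from being chosen after the results are seen.

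**Working it through.** **Inputs.** From the documents: 25 per arm (N = 50), t-test, covariates as listed above. The documents give no alpha, SD, effect size or R², so there is no power figure to reproduce. Assumed: two-sided 0.05, true differences of 0.5, 0.7 and 1.0 SD, and R² from 0 to 30%.

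**t-test.** The standard error in SD units is √(2/25) = 0.283. At 0.7 SD the noncentrality is 0.7/0.283 = 2.475, with 48 df and critical value 2.011. Power is 67.9%.

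**ANCOVA with p = 2 covariates.** The variance is multiplied by (1 − R²) × (N − 3)/(N − 3 − p) = (1 − R²) × 47/45, with 46 df and critical value 2.013. At 0.7 SD the noncentrality is 0.7/√(0.08 × factor):

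| R² | Variance factor | Noncentrality | Power at 0.7 SD |
|---|---|---|---|
| 0% | 1.044 | 2.422 | 65.9% |
| 10% | 0.940 | 2.553 | 70.5% |
| 20% | 0.836 | 2.707 | 75.5% |
| 30% | 0.731 | 2.894 | 80.9% |

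The same steps at 0.5 SD give 41.0% for the t-test and 39.5/43.1/47.4/52.6% for ANCOVA. At 1.0 SD they give 93.4% and 92.3/94.6/96.6/98.2%.

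**Break-even.** On variance alone, (1 − R²) × 47/45 = 1 gives R² = 1 − 45/47 = 4.3%. Allowing for the two lost degrees of freedom, it is 4.4%. With three covariates it is 6.6%.

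**In patients.** At 0.7 SD, ANCOVA at R² of 10/20/30% has the power of a t-test with 26.5/29.7/33.8 per arm. The difference detectable with 80% power is 0.81 SD by t-test and 0.79/0.74/0.69 SD by ANCOVA.

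**NRS as whole numbers from 0 to 10.** Simulation with 5,000 trials per setting, R² set on the underlying scale and split equally between the two covariates, and half the cases laparoscopic (assumed). At 0.7 SD, t-test power is 67% and ANCOVA 66/71/74/79% at R² of 0/10/20/30%. ANCOVA type I error is 4.7 to 5.7%. About 22% of baseline scores are zero in that set-up. With more zeros (4,000 trials, R² of 10%), power goes from 66.3% to 68.1% when about 60% are zero, and from 66.7% to 67.6% when about 89% are zero. The last gain is near Monte Carlo error. At R² of 20% the gain with many zeros is still 4 to 6 points.

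**Opioid totals.** Assumed log-normal, exp(0.8 × latent), 30% preoperative users, yes/no opioid covariate, difference of 0.7 log-SD. On the raw scale, t-test power is 54 to 56% and ANCOVA 54/57/60/65% at R² of 0/10/20/30%. On the log scale the outcome is normal, so the closed-form figures above apply: 68% unadjusted and 81% by ANCOVA at R² of 30%. In this model raw-scale ANCOVA (65%) does worse than an unadjusted t-test on log totals (68%), so the scale matters as much as the covariates.

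**The case against.** The strongest reply is that nothing is broken. An unadjusted comparison is an accepted choice in a randomised trial, it contradicts nothing else in the protocol, and nobody can state the gain because R² is unknown. There are reasons to expect a modest R². Many patients may have little pain before surgery, and the opioid-tolerance exclusion removes the heaviest users. The covariate data are also partly unconfirmed: one list gives a single preoperative score, opioid dose may not be recorded, and approach is an intraoperative field from which the pre-conversion approach must be derived. Finally, adjustment does not supply what the plan lacks more seriously, a named primary outcome and time point.

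All of that stands, and it limits the claim. It does not remove it. At the differences examined the loss is at most 2.0 points, while the gain at 0.7 SD and R² of 30% is 80.9 − 67.9 = 13.0 points, for a few lines of text.

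A reader might infer that the t-test is biased or wrong, or that adjustment is sure to raise power. The documents support neither: allocation is random and blinded, and no passage shows that R² exceeds 4.4%. Nor can one say that the trial misses its power target, because none is stated.

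**Conclusion.** The point holds as a cheap improvement, not as an error. The planned t-tests leave recorded predictors unused, and the consequence is lost efficiency only. Under the stated assumptions at 0.7 SD, a two-covariate ANCOVA changes power by −2, +3, +8 or +13 points at R² of 0, 10, 20 or 30%. The gain at R² of 10% nearly vanishes for NRS if almost all baseline scores are zero. Skewed opioid totals gain little from adjustment on the raw scale. The direction depends on whether R² exceeds 4.4%, which the documents cannot settle. None of these figures applies to time to flatus or bowel movement.

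**What to change.** Before unblinding, write into Data Analysis:

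1. Each NRS outcome is compared by ANCOVA, adjusted for the matching baseline NRS (rest or cough; the baseline rest score for the 12-hour average rating) and for approach before any conversion. A converted case counts as laparoscopic, because randomisation on the day of surgery precedes conversion.
2. PACU and 24-hour morphine equivalents are compared by ANCOVA, adjusted for the same approach and for preoperative opioid use (yes/no if dose is not recorded). The log scale is used if totals are skewed, judged on pooled blinded data, with a small constant fixed in advance if zero totals occur.
3. A missing baseline value is replaced by the mean over both arms, so that no patient is dropped for a missing baseline. This does not deal with missing outcomes, such as PACU scores from patients too drowsy to answer; those need their own rule.
4. Each model keeps these two covariates, and the unadjusted t-test is reported as a sensitivity analysis.
5. Confirm that the case form records baseline NRS both at rest and with coughing.

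Cost: a few lines of text and code, some work to derive the pre-conversion approach and code opioid use, and two degrees of freedom per model. If the covariates explain nothing, power falls by 1.1 to 2.0 points. A third covariate would cost up to about 1 more point, hence two per model. On the log scale the opioid result is a ratio of geometric means, not a difference in means, and the text should say so.
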